15. RStudio Team (2020). RStudio: Integrated Development Environment for R. RStudio, PBC, Boston, MA URL <http://www.rstudio.com/>.

Table 1. Calculation of Standardized Protective Qi Score (PQS)

Category	Parameter	Weight
Cold History	TCM Inquiry (Cold frequency)	25%
Symptoms of PQD	TCM Inquiry (Spontaneous sweating)	16.7%
	TCM Inquiry (Aversion to wind & cold)	16.7%
Sign of PQD	TCM Inspection (Tongue)	8.3%
	TCM Auscultation (Low voice & apathy)	6.7%
	TCM Palpation (Overall Pulse)	10%
	TCM Palpation (Cun Pulse)	16.7%

The PQS were obtained from the standardized protocol shown in Table 2, and the weighting coefficients were based on TCM investigators' clinical experience.

Table2: Standardized criteria for PQS assessment

Candidate Parameter		Method of measurement and scores	
Cold Frequency	TCM Inquiry (Cold frequency)	No cold in the past 2 months	0
		Once in the past 2 months	1
		Twice in the past 2 months	2
		3 times or more in the past 2 months	3
Symptoms of PQD	TCM Inquiry (Spontaneous sweating)	No spontaneous sweating, sweat only with intense physical activities	0
		Sweat with routine physical activities	1
		Sweat heavily with routine physical activities	2
		Sweat with slight physical activities like walking	3
		Sweat spontaneously	4
	TCM Inquiry (Aversion to wind & cold)	No aversion to wind or cold	0
		Aversion to wind	1
		Aversion to cold, but relieved by adding light clothing	2
		Aversion to both cold (but relieved by light clothing) and wind, or susceptible to cold when exposed to wind or cold	3
		Aversion to cold (only relieved by thick clothing that covers whole body); or very easily catch a cold when exposed to wind or cold	4
Sign of PQD	TCM Auscultation (Low voice & apathy)	The participant's voice is loud & clear at a distance of 2m from the investigator	0

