		3 times or more in the past 2 months	3
Symptoms of PQD	TCM Inquiry (Spontaneous sweating)	No spontaneous sweating, sweat only with intense physical activities	0
		Sweat with routine physical activities	1
		Sweat heavily with routine physical activities	2
		Sweat with slight physical activities like walking	3
		Sweat spontaneously	4
	TCM Inquiry (Aversion to wind & cold)	No aversion to wind or cold	0
		Aversion to wind	1
		Aversion to cold, but relieved by adding light clothing	2
		Aversion to both cold (but relieved by light clothing) and wind, or susceptible to cold when exposed to wind or cold	3
		Aversion to cold (only relieved by thick clothing that covers whole body); or very easily catch a cold when exposed to wind or cold	4
Symptoms of Lung Qi Deficiency	TCM Inquiry (Shortness of Breath)	1-10 scale, with 1 indicating the most symptomatic	
	TCM Inquiry (Unwilling to talk)		
Symptoms of Spleen and Heart Qi Deficiency	TCM Inquiry (Limb weakness)	1-10 scale, with 1 indicating the most symptomatic	
	TCM Inquiry (Lack of energy)		
	TCM Inquiry (Low spirit, fatigue)		
Sign of GQD	TCM Auscultation (Low voice & apathy)	The participant's voice is loud & clear at a distance of 2m from the investigator	0
		The participant can be heard & understood at 2m from the investigator, but the voice is recognizably weak.	1
		The participant's voice is clearly low at 2m from the investigator & needs much attention to understand.	2
		The participant can be heard from 2m but need repeated clarification.	3
		The participant cannot be heard with a clear understanding at a distance of 2m.	4
	TCM Inspection (Tongue)	The tongue looks light red with thin white coating and is of proper size.	0
		The tongue looks pale in color with white coating; however, the tongue is of proper size & has no tooth mark on the sides.	1
		The tongue looks pale with white coating. This size is slightly larger than normal. Tooth-marks are visible but are limited to part(s) of the tip and sides of the tongue.	2
		The tongue looks pale with white coating. This size is significantly larger than normal. Tooth-marks are visible along the full length of the tip and sides of the tongue.	3
	TCM Palpation (Overall Pulse ¹)	Normal pulse	0
		Deficient Pulse is detectable but not apparent	1
		Apparent Deficient Pulse	2
	TCM Palpation (Cun Puls ¹)	Normal pulse	0
		The pulse shows characteristics of Floating or Deficient Pulse, but not both.	1

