Appendix I

Participant questionnaire (Qi-related information)

Part I

Do you have a history of **catching** a cold* (*, defined by TCM) in the past year? If no, please proceed to Part II of this section; if yes, please fill out the following blanks.

1. How many times did you **catch** a cold* in the **past year**?
 - i. Once duration:

 - ii. Twice duration of cold #1:
duration of cold #2:

 - iii. 3 times or more duration of cold #1:
duration of cold #2:
duration of cold #3:
duration of other colds:

 - iv. During the above colds*, did you experience any of the following symptoms:
 - Sneezing
 - Coughing
 - Sweating
 - Nasal discharge or congestion
 - Itching or painful throat
 - Headache
 - Aversion to wind and cold
 - General pain and malaise
 - High fever (body temperature > 39.1⁰C)

2. How many times did you **catch** a cold* **last winter (2017 – 2018)**?
 - i. Once duration:

 - ii. Twice duration of cold #1:

duration of cold #2:

iii. 3 times or more

duration of cold #1:

duration of cold #2:

duration of cold #3:

duration of other colds:

iv. During the above colds*, did you experience any of the following symptoms:

- Sneezing
- Coughing
- Sweating
- Nasal discharge or congestion
- Itching or painful throat
- Headache
- Aversion to wind and cold
- General pain and malaise
- High fever (body temperature > 39.1⁰C)

3. How many times did you **catch** a cold* in the **last two months**?

i. Once

duration:

ii. Twice

duration of cold #1:

duration of cold #2:

iii. 3 times or more

duration of cold #1:

duration of cold #2:

duration of cold#3:

duration of other colds:

iv. During the above colds*, did you experience any of the following symptoms:

- Sneezing
- Coughing

- Sweating
- Nasal discharge or congestion
- Itching or painful throat
- Headache
- Aversion to wind and cold
- General pain and malaise
- High fever (body temperature $> 39.1^{\circ}\text{C}$)

4. How many days have elapsed since you last experienced symptoms of a cold*? If you currently have an ongoing cold, write “ongoing”.

Part II

1. Do you have spontaneous perspiration?
 - a. I don't readily sweat, or sweat only with intense physical activities
 - b. I sweat with some slight physical activities like walking
 - c. I sweat spontaneously
 - d. I sweat heavily and instantly with physical activities
 - e. I sweat even without any physical activities

2. Aversion to wind or cold
 - a. No aversion to wind or cold
 - b. Aversion to wind

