Appendix III

Participant questionnaire – Section II (Generic Qi-related information)

Part I

1. Did you catch any cold* (*as defined by TCM) in the past two weeks?
 - a. If no, please proceed to Part II
 - b. If yes: how many times, and how long did it last?
 - v. Once duration:
 - vi. Twice duration of cold #1:
duration of cold #2:
 - c. During the above colds*, did you experience any of the following symptoms:
 - Sneezing
 - Coughing
 - Sweating
 - Nasal discharge or congestion
 - Itching or painful throat
 - Headache
 - Aversion to wind and cold
 - General pain and malaise
 - High fever (body temperature $>39.1^{\circ}\text{C}$)
 - d. How many days have elapsed since you last experienced symptoms of a cold*? If you currently have an ongoing cold, write “ongoing”.

Part II

3. Do you have spontaneous perspiration?
 - a. I don't readily sweat, or sweat only with intense physical activities
 - b. I sweat with some slight physical activities like walking
 - c. I sweat spontaneously
 - d. I sweat heavily and instantly with physical activities
 - e. I sweat even without any physical activities
4. Aversion to wind or cold
 - a. No aversion to wind or cold

- b. Aversion to wind
- c. Aversion to cold, but relieved by adding clothing
- d. Aversion to both cold (but relieved by clothing) and wind, or susceptible to cold* when exposed to wind or cold weather
- e. Aversion to cold (only relieved by clothing that covers whole body), very readily catch a cold* when exposed to wind or cold weather

Part III

- 1. Do you often feel shortness of breath?
- 2. Do you often feel unwillingness to talk?

Part IV

- 1. Do you often feel limb weakness?
- 2. Do you often feel a lack of energy?
- 3. Do you often feel in low spirits?

Part V

- 1. Do you often have a cough?
- 2. Do you often have thin sputum
- 3. Do you often feel timidity

Part VI

- 1. Do you often have poor appetite?
- 2. Do you have loose stools
- 3. Do you often have uncomfortable feeling in the abdomen after eating?

Part VII

- 1. Do you often feel palpitations?
- 2. Do you often feel depressed?

Part VIII

- 1. Do you have frequency of urination?
- 2. Do you often feel soreness of lower back?
- 3. Do you have cold limbs, especially legs?

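### The sweating options on the participant forms do not match the Table 2 and Table 4 scoring levels, and no rule links a form answer to a score

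*Combined protocol and SAP*

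**What the plan says.** Tables 2 and 4 grade sweating identically:

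- 0: "No spontaneous sweating, sweat only with intense physical activities"
- 1: "Sweat with routine physical activities"
- 2: "Sweat heavily with routine physical activities"
- 3: "Sweat with slight physical activities like walking"
- 4: "Sweat spontaneously"

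Appendix I, Part II (screening) and Appendix III, Part II (follow-up) carry one common set of five lettered options. Option a is no ready sweating, or only with intense effort. Option b is "I sweat with some slight physical activities like walking", c is "I sweat spontaneously", d is "I sweat heavily and instantly with physical activities", and e is sweating in the absence of any activity.

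The source of the score is described in two ways. Section 2.4 says the Appendix I questionnaire is used to quantify Protective Qi deficiency, and has Appendix III completed at each follow-up visit. Sections 2.3 and 2.5.1.1 say the practitioner makes the standardized assessment with Tables 1 and 2. No section assigns numbers to options a to e or says how a form answer becomes a table score. Sweating has a weight of 16.7% in the PQS (Table 1) and 10% in the GQS (Table 3).

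**The concern.** Change in PQS from baseline is a primary outcome. A component recorded on one ordinal scale and scored on another needs a stated conversion, and there is none here. At stake are a level that the form cannot return, two options with the same meaning, and an option order that does not follow the table's severity order.

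The next question, on aversion to wind or cold, does run a to e in the same order as Table 2's 0 to 4, with small wording differences. A coder who used a = 0 to e = 4 throughout would be right on that item and wrong on sweating. One declared purpose of the study is to test standardized scores (section 4.0), which the Introduction wants to be less dependent on the individual clinician. An unstated conversion works against that purpose.

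**Working it through.** The plan gives no figure to reproduce, so the check is a comparison of the two scales.

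**Step 1: map the form to the tables.**

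| Option | Content, paraphrased | Table level by wording | Code by position |
|---|---|---|---|
| a | none, or intense effort only | 0 | 0 |
| b | slight effort such as walking | 3 | 1 |
| c | spontaneous | 4 | 2 |
| d | heavy and immediate with effort | 2 (nearest) | 3 |
| e | without any activity | 4 | 4 |

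By wording the reachable levels are 0, 2, 3 and 4, and level 1 has no option. Option d drops the word routine and adds immediacy, so d = 2 is a judgement; 1 and 3 are the neighbouring choices.

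**Step 2: count reversals if answers are coded by position.** Of the 5 x 4 = 20 ordered changes between two different options, count those that improve by wording (level falls) but worsen by position (code rises).

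| Assumed level of d | Improvements by wording | Reversed by position |
|---|---|---|
| 2 | 9 | 2: c to d (4 to 2, coded 2 to 3) and b to d (3 to 2, coded 1 to 3) |
| 1 | 9 | 2: the same two |
| 3 | 8 | 1: c to d (4 to 3, coded 2 to 3) |

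With d = 3, a change from b to d is no change by wording but two levels worse by position. In every case a move between c and e shifts the positional code by two levels with no change in meaning. Positional coding is wrong for b and c whatever d is, and wrong for d unless d = 3.

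**Step 3: size on the score scale.** The plan gives no conversion from 0-4 to 1-10. Assume a linear one: item = 10 - 9 x level / 4.

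- PQS, one level: 9/4 x 0.167 = 0.376, about 0.38 points.
- GQS, one level: 9/4 x 0.10 = 0.225, about 0.23 points.
- c to d with d = 2: PQS +0.75 by table and -0.38 by position, a difference of 3 x 0.376 = 1.13 points in one participant.
- b to d with d = 2: PQS +0.38 by table and -0.75 by position, again a difference of 1.13.

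The Table 1 weights as printed sum to 100.1%. Dividing by that sum leaves one level at 0.38.

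**The case against.** The strongest reply is that the practitioner, not the form, produces the score. Sections 2.3 and 2.5.1.1 say so, and Table 2 calls sweating an inquiry item. The forms could not yield the PQS alone: tongue, pulse and voice are in Appendix II, and Appendix III asks about colds over two weeks where Table 2 asks about two months. A practitioner who asks the Table 2 question directly can record level 1, and no reversal arises.

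Much of this stands. A reader might infer that real improvement will be scored as worsening. The documents do not support that: no section assigns numbers to a to e, and the reversal needs both form-sourced scores and positional coding. A reader might also infer that the item cannot measure change at all. That is not so either, because coding by wording still separates levels 0, 2, 3 and 4. With no response distribution, neither the direction nor the size of any bias in mean change can be given.

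The reply does not remove the inconsistency. Section 2.4 names the Appendix I form as the quantifying tool, and Appendices I and III are the only forms shown that record sweating. If the practitioner does score independently, each visit holds two sweating records on different scales, with no rule for which one counts.

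**Conclusion.** The mismatch is a plain textual fact, present on both forms and against both tables. Its consequences come in tiers:

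- If the practitioner scores Table 2 by direct inquiry, the scores are unaffected and only the documentation is inconsistent.
- If the form is the source and is coded by wording, level 1 cannot be recorded and the level of d is uncertain.
- If the form is the source and is coded by position, b and c are miscoded, as is d if its true level is 2 (or 1). A change from c to d reverses sign, and so does b to d if d is 2 or 1.

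The point values rest on the assumed linear rescale and describe single participants on one of seven PQS items, not a shift in the mean. The correction should be made, but it ranks below the mandatory ones because the sign reversal depends on a coding practice that the plan neither states nor excludes.

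**What to change.** Replace options a to e of the sweating question in Appendices I and III with the five Table 2/4 statements, in order 0 to 4. Position and level then coincide, all five levels can be reached, and no two options share a level.

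Enrollment was planned for March to April 2018 and this version is dated June 2021, so the forms may already have been used. In that case:

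1. State whether the practitioner's Table 2 inquiry or the form is the source of the sweating score. Keep any Table 2 scores the practitioner assigned; do not overwrite them from the form.
2. If the form is the source, code by wording at every visit: a = 0, b = 3, c = 4, d = 2, e = 4, with d = 1 and d = 3 as sensitivity analyses.
3. State that level 1 was not offered.
4. Report PQS and GQS change with and without the sweating item, rescaling the remaining weights to sum to 100%.

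The cost is a wording change on two forms, or one paragraph in section 2.6, a recoding line and an extra table. No visits or staff are added.
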